4.3.4 Safety RP2D Analysis Set

The safety RP2D analysis set is a subset of the All Patients Set and it comprises all patients who received at least 1 full dose at the RP2D level. This will include patients from both phases combined and will be summarized according to disease as per **Table 3** but also including melanoma from Phase I.

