Figure 6-2: Schematic Illustration of a 2-Step IPE Regimen

Rules for the 2-step IPE regimen are as follows:

- The initial target dose level must be a permitted escalation step based on BLRM output and the consensus of the SST
- The initial target dose level must not exceed the 1-step dose-escalation MTD (if established)
- The C1D8 dose level must be at least one dose level below the initial target dose, and must be a dose level that has been evaluated in ≥ 3 patients using a fixed-dose or 1-step IPE regimen, with a decision to escalate based on the BLRM output and SST review of all available relevant data
- Escalation of the target dose in subsequent cohorts may proceed as in the main and 1-step dose escalation:
 - Separate MTD/RP2D may be identified using fixed-dose, 1-step IPE, and 2-step IPE regimens
 - DLT will be attributed to the dose level of the most recently administered dose prior to onset of the DLT (eg, a DLT with onset on C1D4 would be attributed to the C1D1 dose level, while a DLT with onset on C1D10 would be associated to the C1D8 dose level)
- The dose levels for C1D1 and C1D8 remain fixed for all subsequent cohorts
- Patients receiving 2-step IPE must receive the C1D1 and C1D8 doses prior to receiving the target dose
- If a 2-step IPE regimen is evaluated in Phase I, it may be selected for further evaluation in Phase II

An example of how IPE might be implemented is shown in [Figure 6-3](#).

[figure not shown]

Figure 6-3: Representative Escalation Path Incorporating IPE

IPE = intra-patient escalation.

Actual dose levels will be determined using BLRM and must be approved by SST. In this scenario, after 3 patients were enrolled in Cohort 4 and completed DLT evaluation, the recommended next dose per BLRM was 195 mcg. The SST determined that the 195 mcg dose would be better tolerated using a 2-step escalation regimen, and so Cohort 5 was opened with a dose of 30 mcg on C1D1, 100 mcg on C1D8, and 195 mcg as the target dose (weekly starting on C1D15).

In addition, a patient who is enrolled in a lower dose cohort may move to a higher dose cohort once all the following criteria are met:

- The patient has completed at least 3 cycles of treatment
- The patient did not experience any DLT or any \geq Grade 3 treatment-related toxicity
- The patient does not have any ongoing \geq Grade 2 treatment-related toxicity
- The higher dose cohort has completed SST review with a decision to escalate or was determined to be the MTD/RP2D

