6.11 Definition of Maximum Tolerated Dose and Recommended Phase II Dose

The MTD will be determined if the following conditions are met:

1. At least 6 patients have been treated at this dose and associated treatment regimen (ie, fixed-dose, 1-step IPE, or 2-step IPE).
2. The dose has the highest posterior probability that the true DLT rate is in the target interval for toxicity (16%–33%), as predicted by the BLRM. The interval boundaries of 16% and 33% are chosen to be consistent with the traditional 3+3 design toxicity boundary (ie, 1/6 and 1/3).
3. The dose satisfies the EWOC principle (the probability that the DLT rate lies within the excessive toxicity or the unacceptable toxicity window is less than 25%).

The RP2D will be defined as the dose and associated treatment regimen selected for further evaluation in Phase II by the SST. The RP2D will be determined from a synthesis of all data available, including safety, tolerability, PK, pharmacodynamics, and preliminary anti-tumor activity observations from Phase I. The RP2D must not exceed the MTD as determined by the BLRM. A minimum of 6 patients will be treated at the RP2D in Phase I and monitored through the DLT evaluation period before enrollment in Phase II may begin.

During Phase II, following enrollment of at least 12 subjects, if the observed rate of Grade 3 and/or Grade 4 toxicity considered related to IMCnyeso and meeting the definition of DLT is > 30%, a safety teleconference will be convened with the SST to determine if the cohorts should continue enrollment.

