4.2.1 Treatment and Disease Groups for Reporting

The Phase I safety data will be listed, summarized, and analyzed overall and by dose group where dose groups may incorporate pooling of dose levels; the exact extent of pooling will be defined after Phase I actual doses administered are known, and is expected to use the Recommended Phase 2 dose (RP2D) as threshold (see **Table 2**).

Patients who enroll in multiple cohorts will be represented once for each cohort and once in the total/overall study columns for summaries that are based on baseline data (e.g. demographics, medical history). Listing will be presented for patients who are escalated to a higher dose.

Table 2 – Potential Phase I Dose Groups

Treatment Group	Dose Group (Label for TLF Reporting)*	Patients included
IMCnyeso < x mcg QW	< RP2D	All Phase I dose escalation cohorts receiving a dose less than RP2D
IMCnyeso = x mcg QW	= RP2D	All Phase I dose escalation cohorts receiving the same dose as RP2D
IMCnyeso > x mcg QW	> RP2D	All Phase I dose escalation cohorts receiving a dose greater than RP2D

* x mcg is the Recommended Phase 2 Dose (RP2D) where x is determined during Phase I and administered IV over 1-2 hours.

In Phase II, patients will be analyzed according to the disease cohorts laid out in **Table 3**.

Table 3 - Phase II Disease Cohorts at RP2D

Cohort	Disease Cohort
Cohort 1	Advanced NSCLC
Cohort 2	Urothelial Cancer
Cohort 3	Synovial Sarcoma

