4.3.3 Safety Analysis Set (SAF)

The SAF is a subset of All Patients Set and it comprises all patients who received at least 1 full dose or partial dose of IMCnyeso. Patients will be classified in this set according to initial treatment received (see **Table 2**) or disease cohort in Phase II (**Table 3**). The SAF will be used for the safety summary of the study. In Phase I, the SAF will be equivalent to FAS if received doses are equal to planned doses (or sufficiently close to be in the same dose grouping).

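### The pooled Safety RP2D set requires a full RP2D-level dose and admits moved-up patients unflagged, so membership depends on tolerance and pooled toxicity rates tend to be too low

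*SAP*

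**What the plan says.** The set exists only in the SAP, where section 12 says it was added so that some analyses could pool the phases. Its entry rule is that "it comprises all patients who received at least 1 full dose at the RP2D level", and section 4.3.4 adds: "This will include patients from both phases combined". For the main safety set in SAP 4.3.3, "it comprises all patients who received at least 1 full dose or partial dose of IMCnyeso". The full analysis set (4.3.2) uses the same any-dose rule. The per-protocol set (4.3.5) asks for one dose at the RP2D without requiring it to be full.

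The two documents describe the RP2D differently. Protocol 6.11: "The RP2D will be defined as the dose and associated treatment regimen selected for further evaluation in Phase II by the SST". The note to SAP Table 2 (section 4.2.1): "x mcg is the Recommended Phase 2 Dose (RP2D) where x is determined during Phase I". A step-up regimen is a live candidate. Protocol 6.10.1 says "If a 2-step IPE regimen is evaluated in Phase I, it may be selected for further evaluation in Phase II", with a parallel rule for one step, and SAP Table 1 lists cohorts 5 to 7 as intra-patient escalation (IPE). In the two-step form, "Patients receiving 2-step IPE must receive the C1D1 and C1D8 doses prior to receiving the target dose".

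Protocol 6.10.1 also provides that "a patient who is enrolled in a lower dose cohort may move to a higher dose cohort once all the following criteria are met". The criteria are at least 3 completed cycles, no DLT or related Grade 3 or higher toxicity, no ongoing related Grade 2 or higher toxicity, and a destination cohort already cleared for escalation or declared the MTD/RP2D.

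Under SAP section 8, safety is analysed on the safety analysis set separately by phase. Combined outputs on the Safety RP2D set are optional.

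**The concern.** A safety population should be fixed by what patients were assigned and started, not by how well they tolerated it. Here entry turns on completing a dose, and toxicity can prevent that. The same set is also open to patients who reached the RP2D level because they had tolerated a lower dose. The first route removes patients with events from numerator and denominator. The second adds patients screened for tolerance to the denominator. A pooled table meant to describe the chosen dose would then tend to look safer than the experience of those who started it. No reason is given for using a stricter dose rule here than in the neighbouring sets.

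**Working it through.** The documents state no figure for this set, so the check is first a comparison of rules and then an illustration on assumed inputs.

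**Step 1: who is in which set.**

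| Patient | Main safety set | Safety RP2D set |
|---|---|---|
| RP2D-level infusion stopped; a later one completed | in | in |
| RP2D-level infusion stopped; none ever completed | in | out |
| Step-up RP2D, stops during lead-in; level means target dose | in | out |
| Same patient; level means the whole regimen | in | in if a lead-in dose was completed |
| Moved up to the RP2D cohort | in, under initial treatment | in, not flagged |
| Event after a completed RP2D-level infusion | in | in |

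**Step 2: toxicity can cause the losses.** SAP 8.6 foresees infusions stopped part-way. In Protocol Table 6-4, a Grade 3 infusion reaction ends the infusion, and Grade 4 infusion reactions or Grade 4 CRS end treatment. Grade 3 CRS, or a Grade 3 infusion reaction taking more than 6 hours to improve, leads to a dose reduction if treatment continues. Such a patient may never complete a dose at the RP2D level.

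**Step 3: moved-up patients are not held apart.** SAP 4.3.4 does not require assignment to the RP2D from C1D1, does not flag moved-up patients, and does not say which of their events count. SAP 4.2.1 offers only a listing and a counting rule for baseline summaries. Cohorts 1 to 6 in SAP Table 1 hold 4 + 3 + 5 + 3 + 5 + 4 = 24 patients. That is the ceiling on candidates if the cohort 7 target becomes the RP2D. How many qualify is not given.

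**Step 4: illustration (all inputs below except N are assumptions).**
- N, starters on the RP2D: 6 in Phase I (the minimum in Protocol 6.11) plus 3 × 9 = 33, or plus 3 × 24 = 78.
- L, share stopped by a counted toxicity before any full RP2D-level dose: 3% to 15%.
- q, event rate in the rest: 10% to 20%.
- m, moved-up patients, taken to have no event: 0 to 8.

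All starters: L + q(1 − L). Set as defined: q(1 − L)N / [(1 − L)N + m].

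Example with N = 33, L = 10%, q = 10%: all starters 0.10 + 0.10 × 0.90 = 19.0%. Set with m = 0: 10.0%. Set with m = 4: 2.97 / 33.7 = 8.8%.

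Corners of the grid at N = 33:

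| L | q | All starters | Set, m = 0 | Set, m = 8 |
|---|---|---|---|---|
| 3% | 10% | 12.7% | 10.0% | 8.0% |
| 3% | 20% | 22.4% | 20.0% | 16.0% |
| 15% | 10% | 23.5% | 10.0% | 7.8% |
| 15% | 20% | 32.0% | 20.0% | 15.6% |

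The set's rate is lower at every grid point, including all those at N = 78. With m = 0 the gap is L(1 − q): from 0.03 × 0.80 = 2.4 to 0.15 × 0.90 = 13.5 percentage points. If L = 0 nothing is lost. If moved-up patients have the same event rate as the rest, they dilute nothing.

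**The case against.** The strongest reply is that little rests on this set. The main safety analysis keeps every patient with any dose. All Phase II patients are treated at the RP2D, so the Phase II tables already include those who stop early. In Phase I, patients are classified by initial treatment, so moved-up patients stay in their original group. Dose escalation uses the dose-determining set, and the Phase II safety trigger in Protocol 6.11 does not refer to this one. The planned outputs in SAP 14.2 include no Safety RP2D table. All of this stands, and it limits the consequence. It does not repair the definition, because this is the only cross-phase safety population and it will be used as written if a pooled table is made.

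A second reply is that events are rarely lost. Protocol Table 6-4 lets many stopped patients be re-dosed, and CRS after a completed infusion stays in the set. Protocol 1.4 reports no DLT, related Grade 3 or higher event, or discontinuation for an adverse event among 15 patients at 3 to 100 mcg. That is fair, and L could be near zero. But 0 of 15 leaves a one-sided 95% upper bound of 1 − 0.05^(1/15) = 18.1%, and these were fixed doses of at most 100 mcg.

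Third, an exposure-based supplementary set is a legitimate choice. It is, but exposure does not require a *full* dose, and it does not explain mixing in patients selected for tolerance without marking them.

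**Conclusion.** The concern holds in a limited form. As written, the rule selects on tolerance through two routes, and both tend to lower the toxicity rate in any pooled RP2D output. The direction is firmest for DLTs and related Grade 3 or higher events, which moved-up patients cannot have had before the move. The size cannot be estimated, because the documents give neither the number stopped early nor the number moved up.

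A reader might infer four stronger things that the documents do not support:
- That any patient whose first RP2D infusion is stopped is excluded. Only those who never complete a later infusion at that level are.
- That lead-in dropouts are certainly excluded. This needs a step-up regimen as the RP2D and the target-dose reading of its level. SAP Table 2 favours that reading; Protocol 6.11, which defines the RP2D as dose plus regimen, leaves room for the other.
- That the reported rate would fall by some particular factor, such as half. The grid rests on invented inputs and on moved-up patients having no events, although the criteria screen toxicity only before the move.
- That the trial's main safety results or dose decisions are biased. They use other sets.

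**What to change.** Redefine the set in SAP 4.3.4 as all patients, in either phase, assigned from C1D1 to the RP2D dose and regimen who received any full or partial dose, lead-in doses included. State that RP2D has the Protocol 6.11 meaning, so that the single-dose label in SAP Table 2 does not decide membership. Report patients moved up from lower cohorts in a separate display, with events counted from the date of the move.

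The cost is a change of SAP wording and one extra display. The downside is that the reported toxicity rates may be less favourable. No dosing, stopping or move-up rule changes.

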4.3.5 Per-Protocol Set (PPS)

The Per-Protocol Set consists of a subset of FAS patients in Phase II who meet below 4 criteria

1. Presence of measurable disease according to RECIST v1.1
2. At least 1 post-baseline tumor assessment or discontinued prior to the first tumor assessment
3. Received at least 1 dose of planned treatment at the RP2D
4. No violation of key inclusion or exclusion criteria.

Patients in the PPS will be classified according to disease cohort as per **Table 3**.

4.3.6 Dose-Determining Analysis Set (DDS)

The DDS consists of all patients from the SAF in Phase I who meet the criteria in Section 3.4.

This set will be used to guide the dose escalation using actual dose received and will not be an analysis set used in final reporting.

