4 STUDY OBJECTIVES AND ENDPOINTS

Study objectives and corresponding endpoints are shown in [Table 4-1](#).

Table 4-1: Study Objectives and Endpoints

Objectives	Endpoints
Primary - Phase I	
To identify the MTD and/or the RP2D of IMCnyeso, as a monotherapy, when administered weekly to patients with advanced NSCLC, melanoma, urothelial cancer, and synovial sarcoma	Incidence of dose-limiting toxicities Incidence and severity of AE and SAE Changes in laboratory parameters, vital signs, and ECGs Dose interruptions, reductions, and discontinuations
Primary – Phase II	
To assess the preliminary anti-tumor activity of IMCnyeso as monotherapy in advanced NSCLC, urothelial cancer, and synovial sarcoma	BOR as determined by RECIST v1.1
Secondary- Phase II	
To characterize the safety and tolerability of IMCnyeso	Incidence and severity of AE and SAE Changes in laboratory parameters, vital signs, and ECGs Dose interruptions, reductions, and discontinuations
Secondary- Phase I and Phase II	
To assess the preliminary anti-tumor activity of IMCnyeso as monotherapy	Phase I: BOR, PFS, and DoR by RECIST v1.1; OS Phase II: PFS, and DoR by RECIST v1.1; OS
To characterize the PK profile of IMCnyeso as monotherapy	Serum PK parameters (eg, AUC, C _{max} , T _{max} , t _{1/2}) after single and multiple doses
To evaluate the preliminary incidence of anti-IMCnyeso antibody formation following multiple infusions of IMCnyeso	Incidence of anti- IMCnyeso antibody formation and its impact on PK
Exploratory	
[REDACTED]	[REDACTED]

Objectives	Endpoints
[REDACTED]	[REDACTED] [REDACTED] [REDACTED]
[REDACTED]	[REDACTED] [REDACTED] [REDACTED]

AE = adverse event; AUC = area under the curve; BOR = best overall response; CD# = cluster of differentiation #; C_{max} = maximum observed concentration; [REDACTED]; [REDACTED]; DoR = duration of response; ECG = electrocardiogram; [REDACTED]; [REDACTED]; MTD = maximum tolerated dose; NSCLC = non-small cell lung cancer; [REDACTED]; PFS = progression-free survival; PK = pharmacokinetic; RECIST = Response Evaluation Criteria in Solid Tumors; [REDACTED]; RP2D = recommended Phase II dose; SAE = serious adverse event; t_{1/2} = terminal elimination half-life; [REDACTED]; T_{max} = time of maximum concentration; [REDACTED].

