9.5 Primary Analysis Variables

9.5.1 Phase I: DLT

In Phase I, the primary variable is the occurrence of 1 or more DLTs. An adaptive BLRM guided by the EWOC principle will be used to guide dose recommendations and estimate the MTD, as described in [Section 6.10](#) and [Section 13.3](#).

Patients in Phase I who are ineligible for the DDS will be excluded from the primary analysis, although their data will be used for all remaining analyses.

As a supportive analysis in the Phase I dose escalation part of the study, a dose-exposure relationship may be estimated for IMCnyeso via a BLRM to further guide the dose recommendation to targeted exposure of IMCnyeso. From the estimation of the dose-exposure model, the following posterior summaries will be derived for each dose:

- Mean, median, standard deviation, and 95%-credible interval for the exposure
- The probability that the true AUC after first dose of treatment achieves the target exposure

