If the severity of cytokine-mediated AEs tend to become less severe following the initial doses of study drug using a fixed-dose regimen, the SST may initiate step 1 intra-patient escalation regimen, in which a lower dose is given on Cycle 1 Day 1 and a higher (target) dose is given on Cycle 1 Day 8 and beyond. Further details can be found in Section 6.10.1 of the protocol.

A subsection on dose escalation decisions will be included in the CSR, and the BLRM outputs produced for the dose escalation meetings will be included in the CSR appendices.

4 General Statistical Considerations

Categorical data will be summarized using frequencies and percentages. The denominator for all percentages will be the number of patients belonging to the analysis set of interest by dose group or disease cohort according to the particular summary. Percentages will be presented as integer numbers with no decimal part given the small number of patients enrolled. Percentages will not be displayed for 0 frequencies. A row denoted “Missing” will be included in count tabulations where necessary to account for missing values.

For continuous data, the mean, standard deviation (SD), median, minimum (Min) and the maximum (Max) will be presented. For PK, if concentration results below a lower limit of detection (LLOD) and LLOD for a parameter is clinically relevant then it will be included in the calculation of standard statistics with that concentration result set at 0; but for cytokines it will be set at the midpoint between 0 and the LLOD. Minimum and maximum will be presented to the same number of decimal places as the raw data, mean and median will be presented to 1 more

decimal place than the raw data, and standard deviation will be presented to 2 more decimal places than the raw data.

No formal statistical hypotheses will be tested. Where appropriate, two-sided 95% confidence intervals will be presented.

All data summaries and statistical analyses will be performed using the SAS software Version 9.4 or higher (SAS Institute, Cary, NC).

The study day of an event that occurred after or on the first dose date will be calculated as:

Event Date – C1D1 Date + 1

whereas the study day of an event that occurred before the first dose date will be calculated as:

Event Date – C1D1 Date

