7.2.2 Treatment Compliance and Modifications

Study treatment will be administered to the patient at the study site by trained study staff. Patients compliance with the prescribed regimen will be assured as all administrations will be performed by site staff under the supervision of the study investigator or his/her designee. Therefore, no analysis of compliance is planned. However, dose interruptions and reductions may occur (see Section 8.6).

8 Safety Analysis

Safety analysis will be conducted on the SAF for the Phase I dose escalation and separately for the Phase II expansion cohorts. Combined outputs for safety may be produced based on the Safety RP2D Analysis Set.

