8.1 Dose-Limiting Toxicity

The incidence of DLTs is the primary endpoint in Phase I. The specific type and grades of AEs classified as a DLT can be found in the protocol in Section 6.12. The DLT observation period for the Phase I dose escalation cohorts is explained in Section 3.4.

The number and percentage of patients with at least one DLT will be presented by dose group (as defined in Section 4.2.1).

A listing of key information for DLTs will be presented including patient identification number, Preferred Term (PT) of corresponding AE and CTCAE grade. DLT information will be reported and summarized for Phase II whenever appropriate

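### The SAP puts the reported Phase I DLT percentage on all treated patients and bars the Dose-Determining Set from final reporting, while protocol 9.5.1 excludes DDS-ineligible patients from the primary analysis

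*SAP*

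**What the plan says.** **Protocol.** Table 4-1 lists "Incidence of dose-limiting toxicities" first among the Phase I primary endpoints. Section 9.5.1 states that in Phase I "the primary variable is the occurrence of 1 or more DLTs", names the Bayesian logistic regression model (BLRM) as the method that guides dosing and estimates the MTD, and adds that Phase I patients "ineligible for the DDS will be excluded from the primary analysis, although their data will be used for all remaining analyses". Section 9.2.4 defines the DDS by reference to section 6.10.2. Under 6.10.2 a patient is DLT-evaluable in one of two ways: by having a DLT in the 28-day period, or by having none and also receiving at least 3 of the 4 planned doses (at least 2 at the target level) with at least 28 days of observation. Section 6.17 allows non-evaluable patients to be replaced.

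**SAP.** Section 8.1 states: "The incidence of DLTs is the primary endpoint in Phase I". It continues: "The number and percentage of patients with at least one DLT will be presented by dose group". Section 8.1 itself names no set, but the opening of section 8 does: "Safety analysis will be conducted on the SAF for the Phase I dose escalation". The SAF in section 4.3.3 is everyone who received any dose, full or partial. Section 4 fixes the denominator: "The denominator for all percentages will be the number of patients belonging to the analysis set of interest by dose group or disease cohort". Section 4.3.6 keeps the DDS for guiding escalation and says it "will not be an analysis set used in final reporting". Section 12 declares no substantial change from protocol version 4.0 and lists two added analysis sets, neither of which concerns the DDS.

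**The concern.** The protocol and the SAP describe the same quantity, whether a patient had at least one DLT, but appear to attach different populations to it. The protocol drops patients who were not dosed or observed enough to be judged. The SAP retains them, and because they had no in-window DLT they enter the percentage as patients who tolerated the dose.

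At stake is the DLT incidence that a reader of the study report will take as the Phase I primary result. In cohorts of 3 to 6 patients, one patient who left early for an unrelated reason visibly lowers the percentage. A reader comparing it with the 16%–33% target interval in protocol 6.11 would be comparing a diluted figure. Since SAP 12 is silent, nothing warns that the set differs from the one on which the dose was chosen.

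**Working it through.** The plan states no figure of its own to reproduce. The check compares the set rules and then works out the direction and possible size of the difference.

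**Step 1: which patients differ.** The DDS is a subset of the safety set (protocol 9.2.4). By 6.10.2 every patient with a DLT in the 28-day period is in the DDS. So the only patients in the SAF but outside the DDS are those without an in-window DLT who were under-dosed or under-observed.

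**Step 2: direction for in-window DLTs.** Let N be treated patients in a reported group, k the non-evaluable patients and d the patients with an in-window DLT.

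- SAF rate = d/N
- DDS rate = d/(N − k)
- SAF rate = DDS rate × (N − k)/N

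The factor (N − k)/N is at most 1. The SAF rate therefore equals or understates the DDS rate, and is strictly lower exactly when d ≥ 1 and k ≥ 1.

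**Step 3: where a difference could arise.** SAP Table 1 gives 4 + 3 + 5 + 3 = 15 patients in cohorts 1–4 and 5 + 4 + 6 (planned) = 15 in cohorts 5–7. Protocol 1.4 reports no DLT in the 15 patients treated at the cohort 1–4 doses by 22Jan2020, in data described as not fully validated. On that information the rate in each of those cohorts is 0% on either set.

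**Step 4: illustration.** The documents give neither k nor the DLT counts for cohorts 5–7. Assume d = 1 and k = 1 or 2. SAP 4.2.1 and SAP Table 2 also allow cohorts to be pooled below, at or above the RP2D. The last row assumes, for illustration only, that cohort 7 is the RP2D, so that cohorts 1–6 form the lower group: 4 + 3 + 5 + 3 + 5 + 4 = 24.

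| Reported group | N | SAF | DDS, k = 1 | DDS, k = 2 |
|---|---|---|---|---|
| Cohort 5 | 5 | 1/5 = 20% | 1/4 = 25% | 1/3 = 33% |
| Cohort 6 | 4 | 1/4 = 25% | 1/3 = 33% | 1/2 = 50% |
| Cohort 7 (planned) | 6 | 1/6 = 17% | 1/5 = 20% | 1/4 = 25% |
| Cohorts 1–6 pooled | 24 | 1/24 = 4.2% | 1/23 = 4.3% | 1/22 = 4.5% |

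With k = 0 or d = 0 the two sets agree.

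**Step 5: DLTs outside the window.** Protocol 6.12 lets the Study Safety Team count an event outside the evaluation period as a DLT. Such an event in a non-evaluable patient is in the SAF numerator but not in the DDS. With N = 6, k = 1, no in-window DLT and one such event, the SAF gives 1/6 = 17% and the DDS 0/5 = 0%. The result in step 2 therefore holds for in-window DLTs only.

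**The case against.** The strongest reply is that the primary analysis in protocol 9.5.1 is the BLRM. That section names no other method and specifies no descriptive percentage. It sends the excluded patients' data to the remaining analyses, and protocol 9.6.2 puts safety analyses on the safety set. Table 4-1 also lists adverse events, laboratory, vital-sign and ECG changes, and dose modifications as Phase I primary endpoints, so a table of a primary endpoint need not be the DDS-restricted analysis. On this reading SAP 4.3.6 keeps the DDS for its proper use and SAP 12 has nothing to declare. The reading is reasonable, and it means a formal deviation cannot be asserted. It does not change what the percentage measures: patients whom protocol 6.17 treats as replaceable still count as DLT-free.

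Three stronger readings might be inferred, and the documents do not support them.

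- *The SAP leaves the set undefined.* It does not: the opening of SAP 8 assigns the SAF, and 8.1 sits under it.
- *No DDS-based toxicity estimate will reach the study report.* SAP 3.4 places the BLRM outputs from the escalation meetings in the report's appendices. By protocol 6.10 and 13.3.1 those rest on the DDS and give posterior DLT rates by dose. What is missing is an observed DDS-based rate.
- *Gaps such as 25% against 50% are to be expected.* They need unpooled reporting and assumed counts.

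It is also fair to object that a DDS table alone could lose an out-of-window DLT in a non-evaluable patient (step 5). That stands, and the fix has to deal with it.

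**Conclusion.** The point holds as a matter of reporting. The SAP places the Phase I DLT percentage on all treated patients and rules out the set that protocol 9.5.1 attaches to the primary analysis, without declaring it. Whether this formally departs from the protocol depends on whether the primary analysis means the BLRM alone. On either reading the in-window rate can be diluted and cannot be inflated.

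The size cannot be stated. Under the assumption of one DLT and one non-evaluable patient it is 3 to 8 percentage points in cohorts of 4 to 6 (17% against 20%, 25% against 33%). In a pooled group of 24 it is about 0.2 points (1/23 − 1/24 = 0.0018), which disappears when percentages are shown as integers, as SAP 4 requires. It is zero where a group has no DLT or no non-evaluable patient.

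A reader might infer that dose selection is compromised. It is not: escalation and MTD estimation still use the DDS (protocol 6.10, SAP 4.3.6).

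**What to change.** - **SAP 4.3.6:** delete the bar on final reporting, state that the DDS is the set for the primary Phase I DLT summary, and cite protocol 6.10.2 directly for the criteria and the 28-day period. The present reference to SAP 3.4 only leads on to that section.
- **SAP 8.1:** report DLT n/N (%) on the DDS as the primary summary, by cohort and regimen, because protocol 6.11 defines the MTD for a dose together with its regimen. Give the SAF version as supportive. List any DLT that the Study Safety Team declares outside the window in a non-evaluable patient, so that it is not lost.
- **SAP 14.2:** add these tables. SAP 4 promises DLT tables, but the planned list contains none.
- **Alternative:** if the SAF stays as the main set, say so in SAP 8.1 and declare and justify it against protocol 9.5.1 in SAP 12.

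The cost is SAP wording and one extra table. DDS membership is already needed for the BLRM updates, so no new data are required. Reported DLT rates may be slightly higher.
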